# 2.3 Exploratory Objectives

1) To explore drug effects on progression to dementia (based on confirmed progression using DSM-IV criteria)

- a) To explore effects of BMS-708163 on brain atrophy rate as measured by volumetric MRI
- b) To explore and prospectively characterize effects the Clinical Dementia Rating scale (including the CDR-Sum of Boxes score and CDR global score), an instrument designed to measure the severity of cognitive symptoms in daily life, as part of the natural course (in placebo patients) and potential impact of BMS-708163
- c) To explore the correlation of APOE status with BMS-708163 pharmacodynamic (PD) effects (such as on biomarkers and cognition)
- d) To explore Aβ42 CSF Screening cut-off value of > 200 pg/mL versus < 200 pg/mL and Total Tau/AB42 ratio ≥ 0.39 with regard to progression rates and biomarker changes in both the randomized and the non-randomized, observational cohort of subjects
- e) To explore the pharmacodynamic effects of BMS-708163 on CSF biomarkers linked to mode of action (A $\beta$ 38, A $\beta$ 40, A $\beta$ 42), and putative biomarkers of neurodegeneration (total Tau, phosphorylated Tau) and lipid peroxidation (isoprostanes) in AD
- f) To explore the pharmacodynamic effects of BMS-708163 on Cognition as assessed by an Executive Function Test Battery and the ADAS-cog
- g) To explore the pharmacodynamic effects of BMS-708163 on Function in daily living as assessed with the Alzheimer's disease Collaborative Study Activities of Daily Living scale (ADCS-MCI-ADL)
- h) To explore the pharmacodynamic effects of BMS-708163 on progression on the Global Clinical Dementia Rating (CDR global) (ie, progression to a global score of 1)
- i) To explore effects of BMS-708163 on brain amyloid content as measured via PET-amyloid imaging (AV-45) in a subset of subjects at specified sites
- j) To explore the pharmacodynamic effects of BMS-708163 on the subject-reported Outcomes in Cognitive Impairment (PROCOG), an instrument designed to assess severity of impairment and impact on subjects
- k) To assess Notch-mediated (safety related) effects of BMS-708163 on:
  - TFF3 plasma concentrations and its association with gastrointestinal safety signals
  - Lymphocyte mRNA levels of HES-1 and its association with clinical safety signals
  - The immune system (lymphocyte subpopulations; immunoglobulin serum levels)
- 2) To characterize pharmacokinetics (PK) and its relationship with pharmacodynamic (PD) effects:

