Subjects who do not meet the CSF inclusion criteria (CSF A $\beta$ 42 < 200 pg/mL or Total Tau/A $\beta$ 42 ratio of  $\geq$  0.39) but otherwise fulfill the study inclusion criteria may continue to be followed for rating scale visits but will not be randomized to any treatment arm. Given the projected CSF A $\beta$ 42 Screen Failure rate of 50%, it is estimated that approximately 100 subjects will enter the non-randomized observational group. Subjects in this non-randomized observational cohort will serve to provide prospectively collected comparison data regarding CSF cutoff values and progression to dementia rates. Once subjects in this observation cohort progress to a diagnosis of dementia they will be discontinued from the study.

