# 2) Target Population

- c) Subject meets prodromal Alzheimer's disease criteria as defined by:
  - i) Memory complaint by subject or study partner that is verified by a study partner.
  - ii) Abnormal memory function documented by at least 1 of the 4 following criteria:
    - (1) scoring below the education adjusted cutoff on the Logical Memory II subscale (Delayed Paragraph Recall) from the Wechsler Memory Scale Revised (the maximum score is 25):
      - (a) less than or equal to 8 for 16 or more years of education.
      - (b) less than or equal to 4 for 8 15 years of education.
      - (c) less than or equal to 2 for 0 7 years of education. **OR**
    - (2) Free and Cued Selective Reminding Test (FCSRT) Total Recall score of  $\leq$  39 **OR**
    - (3) Free and Cued Selective Reminding Test (FCSRT) Free Recall score of  $\leq 24$  OR
    - (4) Free and Cued Selective Reminding Test (FCSRT) Delayed Free Recall score of  $\leq 8$ .
- d) CSF A $\beta$ 42 levels below 200 pg/mL or Total Tau / A $\beta$ 42 ratio of  $\geq$  0.39. Additionally, subjects who meet all other inclusion/exclusion criteria with the exception of the CSF criteria above, may be eligible to be followed in a non-randomized, observational cohort to assess progression rates [see Section 6.4.4.8]);
- e) Mini-Mental State Exam score between 24 and 30 (inclusive);
- f) Clinical Dementia Rating global score must be = 0.5 at Screening and Baseline **and** the Memory Box score must be at least 0.5 at both Screening and Baseline;
- g) Subjects must have an MRI performed during the screening period, prior to randomization, to allow the results to be available at the baseline visit. Results will be centrally read. To be eligible for the study the MRI results must:
  - i) Be normal (commensurate with age) or demonstrate atrophy consistent with an Alzheimer's disease diagnosis;
  - ii) Reveal no more than mild to moderate white matter disease;
  - iii) Up to 2 lacunar infarcts are acceptable however, no lacunes are permitted in the anterior thalamus, genu of internal capsule, or basal forebrain;

CN156018 Clinical Protocol

- iv) Reveal no cortical infarcts;
- v) Reveal no more than four microbleeds. Note: if an MRI scanner with a field strength > 1.5 T is used, a higher number of microbleeds will be acceptable as determined by the central neuroradiologist.

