# 8.4.3 Efficacy Analyses

Confidence intervals will be reported at the 95% level, if not otherwise specified.

In order to assess the predictive value of baseline CSF biomarkers (A $\beta$ 40, and A $\beta$ 42, total Tau, total Tau/A $\beta$ 42 ratio, and phosphorylated Tau) on progression to dementia, the relationship between each of CSF biomarker and time to progression to dementia will be assessed by separate stratified Cox proportional hazards model on the Randomized Sample. The Cox model will include treatment, age, gender, education and individual baseline biomarker as covariates and ApoE4 status and baseline status of acetylcholinesterase inhibitor treatment as stratified variables. The parameter estimate and 95% CI for the hazard ratio for one unit increase in the biomarker will be reported. Patients who do not have progression to AD will be censored on their last visit date.

In order to validate  $A\beta42$  screening cutoff point of 200 pg/mL, stratified logistic analysis will be carried out on the combined dataset of placebo group and observational cohort. The logistic model will have progression to AD (yes/no) as a binary dependent variable and age, gender, education and  $A\beta42$  screening value as covariates and ApoE4 status and baseline status of acetylcholinesterase inhibitor treatment as stratified variables.

Time to progression to dementia will be obtained from Kaplan-Meier maximum likelihood estimates for each treatment group on the Randomized Sample.

For each of the continuous efficacy outcome measurements (CDR-SB and ADAS-Cog, etc), the change from baseline to post-baseline scores (up to 24 months) over time from the Randomized Sample will be analyzed using a linear mixed effects model repeated measures (MMRM) with maximum likelihood estimation. The model will include treatment, time, baseline primary efficacy score, the interaction between baseline primary efficacy score and time, baseline MRI volume, APOE status, baseline status of acetylcholinesterase inhibitor treatment and the interaction between treatment and time as covariates. Time is classified into months (3, 6, 9, 12, 15, 18, 21, and 24) and treated as a categorical variable. An unstructured covariance matrix will be used to represent the correlation of the repeated measures within each subject. Model based adjusted mean change score from baseline (LS means) at each study month and 95% CI for the treatment difference will be reported.

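### The only combined-cohort cut-off model enters Aβ42 as a value and leaves out the tau/Aβ42 ratio, so it tests neither of the two cut-offs named in exploratory objective 1d

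*Protocol*

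**What the plan says.** **Entry rule.** Protocol Section 4.2.1, item 2) d, admits a subject to randomization with CSF Aβ42 "levels below 200 pg/mL or Total Tau" over Aβ42 of 0.39 or more. Section 4.1 and the first footnote to Table 6.1-3 place subjects who fail this two-part rule, but are otherwise eligible, in the non-randomized observational cohort. Section 4.1 says that this cohort "will serve to provide prospectively collected comparison data regarding CSF cutoff values and progression to dementia rates".

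**Objective.** Section 2.3, item 1d, concerns, for Aβ42, the "CSF Screening cut-off value of > 200 pg/mL versus < 200 pg/mL and Total Tau/AB42 ratio ≥ 0.39 with regard to progression rates". The same item covers change in biomarkers, and it applies to randomized and observational subjects alike.

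**Analysis.** Section 8.4.3 describes one model on the combined placebo and observational data. Its stated aim is to validate the Aβ42 "screening cutoff point of 200 pg/mL, stratified logistic analysis will be carried out on the combined dataset of placebo group and observational cohort". The outcome is progression yes/no. The covariates are age, gender, education and the Aβ42 "screening value as covariates and ApoE4 status and baseline status of acetylcholinesterase inhibitor treatment as stratified variables".

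**The ratio elsewhere.** The tau/Aβ42 ratio is one of five baseline biomarkers whose relationship with "time to progression to dementia will be assessed by separate stratified Cox proportional hazards model on the Randomized Sample". The hazard ratio is reported per unit of biomarker.

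**The concern.** The objective poses two threshold questions, and the observational cohort exists to supply the comparison group for them. The analysis section answers neither. The model meant to validate 200 contains nothing that depends on the number 200, and the ratio criterion, which can by itself admit a subject to randomization, is absent from it.

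If Section 8.4.3 were followed as written, a clear Aβ42 slope could be reported as support for the 200 cut-off when it would look much the same for any nearby cut-off. Nothing could be said about 0.39 from data that include subjects on both sides of the entry rule. Objective 1d would close without an answer although the data had been collected.

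**Working it through.** The protocol states no power, sample size or effect figure for this analysis, so there is no figure of its own to reproduce. The check is mainly logical.

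**Step 1. Who is in the combined dataset.** The entry rule gives four cells:

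| Cell | Aβ42 (pg/mL) | tau/Aβ42 | Status under the rule | In the dataset as |
|---|---|---|---|---|
| 1 | below 200 | 0.39 or more | randomized | placebo |
| 2 | below 200 | below 0.39 | randomized | placebo |
| 3 | 200 or more | 0.39 or more | randomized, on the ratio alone | placebo |
| 4 | 200 or more | below 0.39 | not randomized | observational |

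A subject in cell 3 has total tau of at least 0.39 × 200 = 78 pg/mL.

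**Step 2. What the planned model tests.** Within strata of ApoE4 and cholinesterase inhibitor use, it is

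log-odds(progression) = intercept + age + gender + education + β × (Aβ42 value).

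The odds ratio per unit of Aβ42 is the same on either side of 200. Testing β = 0 tests a trend. Neither the estimate nor the test changes if another cut-off is substituted, so the model cannot validate 200.

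**Step 3. Where 0.39 could be tested.** The Cox models use the Randomized Sample, which holds cells 1 to 3 and no cell 4, and take the ratio per unit. The Kaplan-Meier estimates are also on the Randomized Sample, by treatment group. No stated analysis sets 0.39 or more against below 0.39 with cell 4 included.

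**Step 4. Which indicators the dataset can support.**
- Aβ42 below 200: cells 1 and 2 against 3 and 4. Placebo subjects lie on both sides if cell 3 is not empty.
- Ratio 0.39 or more: cells 1 and 3 against 2 and 4. Placebo subjects lie on both sides if cell 2 is not empty.
- Either criterion: cells 1 to 3 against 4. This is the same variable as placebo against observational.

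**Step 5. Can a size be given?** Inputs from the protocol are 135 placebo subjects (Section 8.1), about 100 observational subjects (Section 4.1) and 25% progression per year in prodromal AD (Section 4.4), hence 1 − 0.75² = 43.75% over two years. Three inputs are assumed: the share f of placebo subjects in cell 3, a cell 4 rate of 5% or 10% per year (1 − 0.95² = 9.75%, or 1 − 0.90² = 19.0%), and a two-year horizon. The figures are unadjusted odds ratios (OR) for two-group contrasts, neither of which the plan specifies.

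*Case A: cell 3 progresses at 25% per year.* The entry-rule contrast is (0.4375/0.5625) ÷ (0.0975/0.9025) = 7.20, or 3.32 with 10% per year. At f = 20%, cell 3 has 27 subjects and the group at 200 or more has 127. Its risk is (100 × 0.0975 + 27 × 0.4375)/127 = 17.0%, or 24.3% with 10% per year. The OR for the 200 contrast is as follows.

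| f | Cell 4 at 5%/year | Cell 4 at 10%/year |
|---|---|---|
| 0% | 7.20 | 3.32 |
| 10% | 4.86 | 2.77 |
| 20% | 3.80 | 2.43 |
| 30% | 3.20 | 2.20 |
| 40% | 2.81 | 2.03 |

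*Case B: cell 3 progresses like cell 4.* The 200 contrast stays at 7.20 or 3.32 for any f. The entry-rule contrast is now the weaker one: at f = 20% its positive side has risk (108 × 0.4375 + 27 × 0.0975)/135 = 36.9%, OR 5.42; with 10% per year, 38.8% and OR 2.70.

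*Case C: f = 0.* The two contrasts are identical.

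The size depends on f, and the direction depends on how cell 3 progresses. The documents give neither.

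**The case against.** **Detail for the SAP.** Objective 1d is one of many exploratory objectives in a trial whose primary objective is safety, and a parallel ratio model could sit in an SAP that is not shown. The low rank of the objective stands and limits the weight of this point. The SAP argument is weaker, because Section 8.4.3 does not leave the analysis open: it fixes the aim, dataset, outcome, covariates and strata, and these do not match the objective.

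**The ratio is modelled.** True, in the Cox analyses. But those are per unit and exclude everyone who failed the entry rule, so they cannot assess 0.39 as a cut-off between subjects admitted and subjects turned away.

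**Dilution.** A reader might infer that ratio-only placebo subjects sit on the wrong side of 200 and pull that contrast towards no effect. The documents do not support this as a fact. The plan states no contrast at 200 to be diluted. The 25% rate describes prodromal AD in general, and assuming it for ratio-only subjects presumes the answer to objective 1d; Case B reverses the direction. And for validating 200 itself, a subject with Aβ42 of 200 or more belongs on that side whatever the ratio. If such subjects progress, that is a finding about the cut-off.

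**The composite rule as the main validation.** A reader might want the either-criterion contrast as the headline result. On this dataset it is fully confounded with cohort. The visit schedules differ (Tables 6.1-1 and 6.1-2 against 6.1-3), and observational subjects leave at dementia (Section 4.1) while randomized subjects continue (Section 4.4).

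**Phase 3.** A reader might infer that this model drives Phase 3 selection. Section 8.5 ties Phase 3 planning to interim analyses and does not mention this model.

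**Conclusion.** The mismatch is established from the text alone. Objective 1d names two cut-offs and entry uses either one, but the only combined placebo and observational model is aimed at 200, enters Aβ42 as a value, and so tests neither. No stated analysis that includes subjects who failed the rule uses 0.39. This conclusion needs no assumption about progression rates.

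No numerical bias should be attached to it. The ratio-only share and those subjects' progression are undocumented, and plausible values move the comparison in either direction or leave it unchanged. The point is worth correcting because the present text leaves a stated objective unanswered, but it concerns an exploratory question and does not touch the primary safety assessment.

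**What to change.** In Section 8.4.3, on the same placebo plus observational dataset and with the same covariates and strata:

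1. Fit the logistic model with an indicator for Aβ42 below 200 pg/mL (against 200 or more, so that the split matches the entry rule).
2. Separately, fit it with an indicator for tau/Aβ42 of 0.39 or more.
3. Report the number of placebo subjects who entered on the ratio alone, and their progression.
4. If the either-criterion contrast is shown, present it descriptively and state that it is fully confounded with cohort, with different schedules and exit at dementia in the observational group.

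The model on the Aβ42 value can stay, described as a trend analysis. The two separate indicators are still partly confounded with cohort, because every subject negative on both criteria is observational. The report should say so and give the count in each of the four cells.

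The cost is a few extra exploratory model runs. Table 6.1-1 already schedules the CSF biomarkers at Screening, and the entry rule needs both values, so no new data are required.

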Additionally all subjects who previously discontinued from this study (ie, those who did not participate in the long-term follow-up) but were exposed to greater than one month (31 days) of treatment with avagacestat should be contacted by the site and scheduled to complete the 24 Week Post Treatment/Study Termination Follow-up Visit for a comprehensive skin examination by a dermatologist (or dermatologic physician's assistant in the United States), irrespective of whether they received. a comprehensive skin examination with a dermatologist (or dermatologic physician's assistant in the United States) at the end of study treatment.

The study is a multi-center, randomized, double-blind, 2-arm, placebo-controlled, parallel-group study in patients with prodromal Alzheimer's disease to evaluate safety, tolerability, pharmacodynamic and pharmacokinetic effects of once-daily dosing of BMS-708163 for a minimum of 104 weeks (refer to Study Schematic in Figure 4.1-1 above).

The treatment period for the study will be a minimum of 104 weeks (2 years). Randomized subjects may continue in the study beyond 104 weeks of treatment (up to an estimated maximum of 220 weeks of treatment) until the last randomized subject has had the opportunity to receive study medication for approximately 104 weeks. Thus, given the recruitment period of approximately 27 months, the overall duration of study treatment is expected to last between 104 and 220 weeks for a given subject. The study treatment phase will end once the last randomized subject has completed approximately 104 weeks of treatment (estimated to occur by September, 2013). All subjects still receiving study medication at the time last patient last

Revised Protocol No.: 10

treatment is determined will end treatment and be followed in the Safety Follow-up Visits (4 Weeks and 12 Weeks post end of treatment visit; refer to Section 6.1.1.7).

After assessments of eligibility during the maximum 75 day screening period, subjects will undergo baseline safety and PD assessments. In a subset of subjects, at selected centers, subjects may be consented for 24-hour intensive PK assessments. In another subset of sites, subjects may be consented for PET imaging assessments at pre-specified visits (delineated in a separate, site-specific amendment).

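### The logistic model meant to validate the Aβ42 200 pg/mL cut-off contains no cut-off term, and its yes/no outcome is unprotected against follow-up that differs between the placebo group and the observational cohort

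*Protocol*

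**What the plan says.** Protocol Section 8.4.3 gives the purpose and dataset of the analysis: for the "screening cutoff point of 200 pg/mL, stratified logistic analysis will be carried out on the combined dataset of placebo group and observational cohort". It then fixes the outcome, "The logistic model will have progression to AD (yes/no) as a binary dependent variable", and the predictors. These are age, gender, education and the Aβ42 "screening value as covariates and ApoE4 status and baseline status of acetylcholinesterase inhibitor treatment as stratified variables". The paragraph names no indicator for Aβ42 below versus at or above 200 pg/mL, no time horizon and no follow-up term.

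Other places that bear on it:

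- Section 2.3, objective 1d, asks for a comparison of Aβ42 above versus below 200 pg/mL, and of the Total Tau/Aβ42 ratio at 0.39, with regard to progression rates in the randomized and observational subjects.
- The preceding paragraph of Section 8.4.3 uses a stratified Cox model for the secondary objective and handles follow-up: "Patients who do not have progression to AD will be censored on their last visit date". That model covers the Randomized Sample only and reports a hazard ratio per unit of biomarker. Kaplan-Meier estimation is also limited to the Randomized Sample.
- Section 4.1 says of randomized subjects that "the overall duration of study treatment is expected to last between 104 and 220 weeks for a given subject", and then describes the early termination.
- Section 4.1 says of the observational cohort: "Once subjects in this observation cohort progress to a diagnosis of dementia they will be discontinued from the study". Table 6.1-3 gives it 12-weekly visits. The text at hand states no duration for this cohort; Section 6.4.4.8, which the table cites for detail, is not part of that text.
- Section 8.2 places efficacy analyses at the 104-week endpoint and at each study month, on observed cases, in the paragraph that sets the Randomized Sample as the default.

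**The concern.** There are two separate difficulties.

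First, the model does not match its purpose. A coefficient for the Aβ42 value says whether progression becomes more or less likely as Aβ42 rises. It says nothing specific about 200 pg/mL, and a significant slope could be reported as validation of a cut-off that was never examined.

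Second, a yes/no outcome without a horizon depends on how long each subject was watched. This matters more than usual here because of the entry rule. Section 4.2.1 randomizes subjects with Aβ42 below 200 pg/mL or a Total Tau/Aβ42 ratio of at least 0.39, and the remaining eligible subjects may enter the observational cohort. In the pooled dataset, everyone below 200 pg/mL is therefore a placebo subject and every observational subject is at or above 200. The only placebo subjects on the observational side of the cut-off are those admitted by the ratio alone. If the two cohorts are followed for different lengths of time, that difference appears in the Aβ42 coefficient.

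At stake is the use of about 100 observational subjects. Section 4.1 says they are followed to provide comparison data on CSF cut-off values and progression.

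**Working it through.** **Inputs from the protocol.** Progression of 25% per year (Section 4.4); randomized follow-up of 104 to 220 weeks with about 27 months of recruitment (Section 4.1); 135 subjects per arm (Section 8.1); about 100 observational subjects (Section 4.1). The protocol states no power or effect size for this analysis, so there is none to reproduce.

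**Reproducing the follow-up range.** 104 + 27 × (365.25/12)/7 = 104 + 117.4 = 221.4 weeks, against 220 stated. The roughly two-fold planned spread is confirmed.

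**How far yes/no status depends on follow-up.** P(progressed by w weeks) = 1 − 0.75^(w/52.18).

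- 60 weeks: 28.2%, odds 0.392
- 104 weeks: 43.6%, odds 0.774
- 220 weeks: 70.3%, odds 2.363

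With identical hazards, the odds ratio from follow-up alone is 2.363/0.774 = 3.05 for 220 versus 104 weeks, and 0.774/0.392 = 1.97 for 104 versus 60 weeks. These are comparisons of fixed follow-up times, not predictions of the trial's result.

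**Simulation under no Aβ42 effect.** 135 placebo and 100 observational subjects, 600 replicates, constant hazards, uniform follow-up. Assumptions not in the protocol: 80% of placebo subjects below 200 pg/mL, the Aβ42 distributions, and the observational follow-up ranges (also the placebo range in the last row). The logistic fits omit the other covariates and strata. The odds ratio is for below versus at or above 200 pg/mL; the false-positive rate is for the Aβ42 value, as planned. The rate ratio is events per person-time, standing in for a Cox model.

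| Follow-up, weeks (placebo; observational) | Logistic OR | False-positive rate | Rate ratio |
|---|---|---|---|
| 104–220; 104–220 | 1.01 | 4.2% | 1.00 |
| 104–220; 60–104 | 2.05 | 76% | 1.01 |
| 104–220; 24–156 | 1.92 | 68% | 1.00 |
| 24–156; 104–220 | 0.51 | 73% | 0.99 |

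Unequal follow-up that is distributed alike in both cohorts does no harm under the null. Follow-up that differs by cohort can push the estimate either way. A logistic model at a common 104-week horizon that everyone reaches is also sound (OR 1.00, false-positive rate 4.5%). With a true ratio of 2, the time-based estimate was 1.99 to 2.03 in each scenario tried.

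**Does the slope test the cut-off?** At a 104-week horizon with complete follow-up, data with a smooth gradient and no threshold gave a significant Aβ42 coefficient in 93% of runs. Data with a true step at 200 pg/mL (hazard ratio 2) gave one in 73%. A significant slope does not distinguish the two. A below/above contrast alone does not show that 200 is the best threshold either: the rate ratio was 1.98 in the smooth data and 1.99 in the step data. It does give the comparison that objective 1d names.

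**The case against.** The strongest reply is Section 8.2. If its 104-week endpoint governs this model, the horizon is fixed and the 220-week figure falls away. That is a fair reading and would limit the spread. However, the statement sits with the Randomized Sample default, while this analysis names a different dataset and repeats no horizon. It also leaves open what happens to subjects who stop before week 104 or were cut short by termination. If observed cases means status observed at week 104, observational progressors could drop out of the analysis because they have already left, while placebo progressors remain in follow-up (Section 4.4).

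A reader might infer that the model gives a biased association. The documents do not support that. Bias under the null needs follow-up that differs by cohort or with Aβ42, and no observational duration is at hand to show that it does. Nor does any section say that a subject lost early is coded as not progressed. The rule that observational subjects leave at dementia does not itself distort a yes/no outcome, since they are already events.

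It is also fair that screening value does not strictly exclude a dichotomy, and that sensitivity, specificity and coding rules may lie in a SAP that is not shown. The continuous reading remains the natural one beside the per-unit Cox model. The model form and outcome are fixed in the protocol, so the point is more than missing detail.

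Finally, the objective is exploratory, the primary objective is safety, and the secondary biomarker analysis already uses a Cox model. This stands, and it limits the severity.

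**Conclusion.** The concern holds in two parts of unequal strength. The model as written tests a trend in Aβ42, not the 200 pg/mL cut-off, and does not deliver the contrast in objective 1d. This rests only on the natural reading of screening value as continuous.

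The association is also unprotected against follow-up that differs between cohorts, because cohort and cut-off are tied by the entry rule. The potential effect is large: an odds ratio of about 3 for 220 versus 104 weeks at 25% per year. Its actual size and direction are unknown, and it is nil under the null if both cohorts are followed alike. The simulated odds ratios of 0.51 to 2.05 rest on assumed follow-up patterns and show only what could happen.

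Severity is moderate. The trial's safety conclusions and its secondary biomarker analysis are not affected.

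**What to change.** In Section 8.4.3, replace the logistic model with a stratified Cox model on placebo plus observational subjects. Keep the same covariates and strata, and censor at the last progression assessment. Then:

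- make Aβ42 below 200 versus at or above 200 pg/mL the tested term;
- fit Total Tau/Aβ42 at or above 0.39 versus below 0.39, as objective 1d asks;
- report Kaplan-Meier progression at week 104 by CSF group;
- keep continuous Aβ42 as a supporting fit, and do not describe a significant slope or contrast alone as validation of 200 pg/mL.

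Censoring-adjusted sensitivity and specificity at 200 pg/mL would be a useful optional addition. A table of follow-up time by cohort would let readers judge how far the cohorts differ. The Cox model still assumes that censoring is unrelated to the risk of progression, given the covariates.

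The cost is wording and programming. Progression assessments are scheduled in both cohorts (Tables 6.1-1 to 6.1-3) and the CSF values come from screening, so no new data are needed. If the SAP already sets a contrast, a horizon and rules for early stopping, the protocol text should be brought into line with it.
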